Wound Assessment			x	X				X
Pain Assessments ³	X	X	X	X	X	x	X	X
Quality of Life Questionnaires ⁴	X			Х	X	х	х	X
Daily Pain Medication Diary and Concomitant Medication Log ⁵	х	Х	х	х	Х	Х	х	х
Daily Pain Diary	X	X	X	X	X	X	X	X
Adverse Events		X	х	x	X	X	x	X
	nstances. Visit 1 and							

^{*}Note: In some instances, Visit 1 and Visit 2 can occur on the same day.

Vital signs to include weight, seated systolic/diastolic BP measured in millimeters of mercury (mm Hg), HR (beats per minute), respiration rate (breaths Vital signs to include weight, seated systolic/diastolic BP measured in millimeters of mercury (mm Hg), HR (beats per minute), respiration rate (breaths per minute), and temperature in degrees Celsius (°C). Obtain at the beginning of each visit before any additional assessments are completed. Height will only be recorded one time at visit 1

2 Comparative study only

3 Pain Assessments: VAS and PROMIS® (for V2 Operative Day 0, VAS and PROMIS® performed prior to nerve block, nerve block oNLY if nerve block is performed during screening visit).

4 Quality of Life Questionnaires include: FHSQ

Beile Provided the Provided Provide

^{5.} Daily Pain Medication Diary (including quantity, quality and class of pain medications) related to the nerve injury should be collected during Screening and Operative day and any changes/additions should be collected during the study.

6. Definitions and Terminology

Baseline

Baseline may be considered to be Day 0 (day of the procedure) or the screening period prior to Day 0 depending on appropriateness for the analysis.

Baseline Value

For purposes of analysis, the baseline value is defined as the value captured at the baseline assessment. If this value is not available, the most recent value obtained prior to the repair will be used for the baseline value.

Change from Baseline

Change from baseline will be calculated as post-baseline value – baseline value, unless otherwise noted.

Study Day

Study Day is defined relative to Day 0: Study Day = event date - date of Day 0.

Days on Study

Days on Study is the number of days from Day 0 to the date of study completion or early termination.

Completed Subjects

The treatment period is defined as the time period during which subjects are expected to be evaluated post implantation up to 12 months. Subjects who are evaluated at the last scheduled visit determined by the investigator at each site for each patient will be defined as study completers.

Lost to Follow-Up

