For subjects who have not completed the study, who cannot be contacted, and who do not have a known reason for discontinuation (e.g., withdrew consent or adverse event, etc.), the reason for discontinuation will be "lost to follow-up".

Subject Non-Compliance

A subject is considered noncompliant if they fail to return for follow-up.

The Visual Analog or Analogue Scale for Pain

This pain scale is designed to present to the respondent a rating scale with minimum constraints. Respondents will mark the location on the 100-millimeter line corresponding to the amount of pain they experienced. VAS data are recorded as the number of millimeters from the left of the line with the range 0-100.

Patient Reported Outcome Measurement Information System Questionnaires

The PROMIS questionnaire is a set of person-centered measures that evaluates and monitors physical, mental, and social health in adults and children. Measures are applicable to the general

population and to those with chronic conditions. For this study, PROMIS measures will be used to monitor a subject's physical health/pain. The following six scales will be measured¹:

- Physical function
- Pain intensity
- Pain interference
- Fatigue
- Sleep disturbance
- Pain behavior

For each scale, raw scores are calculated by summing each individual question score. Raw scores are converted to a standard score with a mean of 50 and standard deviation of 10. The score is not valid if any items are missing. Conversion tables are listed in Appendix B.

Foot Health Status Questionnaire

The FHSQ was developed to help better measure responsiveness in overall foot health status. Four scales will be measured²:

- Foot Function
- General Foot Health
- Footwear
- Foot Pain

Each scale has a score ranging from 0 to 100, with higher scores representing better foot health and quality of life. When fewer than 50% of responses for any one scale are missing, any missing values for that scale are assigned to the average value of the non-missing questions.

Scoring will be calculated by transforming the raw scores for each sub-domain into an easily interpretable 0-100 scale, with 0 indicating poorest foot health and 100 representing no problems. The following formula was used to convert the raw scores for each sub-domain:

$$X = \left(\frac{X_{raw} - X_{worst}}{X_{optimal} - X_{worst}}\right) \times S_{optimal}$$

where,

 X_{raw} = Total score of the sub-domain

 X_{worst} = Score of the poorest state of foot health

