7.3. Handling of Missing Data and Protocol Violations

Every effort will be made to obtain the VAS pain score data at each scheduled evaluation from all participants who have been randomized, especially at 12 months, since this is the primary efficacy endpoint (PEE). Missing data will be imputed for the primary endpoint only.

All other endpoints will be analyzed with the data available.

No accommodation will be made for a treatment protocol violation unless the proportion of major violations exceeds 5%. In this case, a sensitivity analysis will be done for the primary endpoint only comparing the results when all participants are included, and when those with major protocol violations are excluded. If the results differ, the analysis with the participants included will be the primary analysis.

Major protocol violations include:

- 1. Treating the participant with a non-study treatment or with a study treatment to which the participant was not randomized.
- 2. Assessing an endpoint by a method other than described in the clinical investigational plan (CIP).
- 3. Failing to report a primary endpoint for any reason other than the death of the participant or the participant leaves the study unrelated to the study treatment.

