9.2. Secondary Efficacy

9.2.1. Endpoints and Analyses

For the comparative study, all secondary endpoints will be summarized by visit with descriptive statistics by treatment group and using a comparative analysis.

	Endpoint	Analysis
1.	The change from baseline of PROMIS Pain Behavior	The treatment groups' scores will be
	Scale score at Month 12	compared with a t-test.
2.	The change from baseline of FHSQ in the General	The treatment groups' scores will be
	Foot Health Scale score at Month 12.	compared with a t-test.
3.	The change from baseline of quantity, quality and	The MME will be compared in the
	class of pain medication use as quantified by MME	treatment groups using a t-test.
	dosing at Month 12.	
4.	The change from baseline of quantity, quality and	The MQS score will be compared in
	class of pain medication use as quantified by the	the treatment groups using a t-test.
	MQS score at Month 12.	
	`	
5.	Recurrence of symptomatic neuroma at Month 12.	Proportion of patients with recurrence
	(Note: Assessments at each visit will be independent.	will be compared between the
	For example, it is possible for a subject to have a	treatment groups using a Fisher's
	recurrence at Month 3 and not have a recurrence at	exact test.
	Month 6.)	

Endpoint	Analysis
6. The Area Under Curve (AUC) of daily pain diary	The AUC will be compared in the
scores and VAS scores during the 12 months	treatment groups using a t-test or other
following the procedure.	appropriate statistical test as
	determined by a biostatistician.

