16	49.2	1.8
17	50.4	1.8
18	51.5	1.7
19	52.5	1.7
20	53.6	1.7
21	54.6	1.7
22	55.6	1.7
23	56.6	1.7
24	57.5	1.7
25	58.5	1.7
26	59.4	1.7
27	60.4	1.7
28	61.3	1.7
29	62.3	1.7
30	63.3	1.7
31	64.3	1.7
32	65.3	1.7
33	66.4	1.7
34	67.5	1.7
35	68.6	1.7
36	69.8	1.8
37	71	1.8

38	72.4	2
39	74.2	2.4
40	77.8	3.7

Sleep Disturbance		
Raw Summed Score	T-score	Standard Error of T-Score
8	28.9	4.8
9	33.1	3.7
10	35.9	3.3
11	38.0	3.0
12	39.8	2.9
13	41.4	2.8
14	42.9	2.7
15	44.2	2.7
16	45.5	2.6
17	46.7	2.6
18	47.9	2.6
19	49.0	2.6
20	50.1	2.5
21	51.2	2.5
22	52.2	2.5
23	53.3	2.5
24	54.3	2.5
25	55.3	2.5
26	56.3	2.5
27	57.3	2.5
28	58.3	2.5
29	59.4	2.5
30	60.4	2.5
31	61.5	2.5
32	62.6	2.5
33	63.7	2.6
34	64.8	2.6
35	66.1	2.7
36	67.5	2.8
37	69.0	3.0
38	70.8	3.2
39	73.0	3.5

40	76.5	4.4
. 0	, 0.0	** *

20 32.9 0.53 21 38.0 0.38 22 40.6 0.33 23 42.4 0.30 24 43.8 0.27 25 45.0 0.25 26 46.0 0.23 27 46.9 0.21 28 47.7 0.20 29 48.4 0.19 30 49.0 0.18 31 49.6 0.18 32 50.2 0.17 33 50.7 0.16 34 51.2 0.16 35 51.7 0.16 36 52.1 0.15 37 52.6 0.15 38 53.0 0.15 39 53.4 0.15 40 53.8 0.14 41 54.2 0.14 42 54.6 0.14 43 55.0 0.14 45 55.7	Pain Behavior		
21 38.0 0.38 22 40.6 0.33 23 42.4 0.30 24 43.8 0.27 25 45.0 0.25 26 46.0 0.23 27 46.9 0.21 28 47.7 0.20 29 48.4 0.19 30 49.0 0.18 31 49.6 0.18 32 50.2 0.17 33 50.7 0.16 34 51.2 0.16 35 51.7 0.16 36 52.1 0.15 37 52.6 0.15 38 53.0 0.15 39 53.4 0.15 40 53.8 0.14 41 54.2 0.14 42 54.6 0.14 43 55.0 0.14 44 55.3 0.14 45 55.7	Raw Summed Score	T-score	Standard Error of T-Score
22 40.6 0.33 23 42.4 0.30 24 43.8 0.27 25 45.0 0.25 26 46.0 0.23 27 46.9 0.21 28 47.7 0.20 29 48.4 0.19 30 49.0 0.18 31 49.6 0.18 32 50.2 0.17 33 50.7 0.16 34 51.2 0.16 35 51.7 0.16 36 52.1 0.15 37 52.6 0.15 38 53.0 0.15 39 53.4 0.15 40 53.8 0.14 41 54.2 0.14 42 54.6 0.14 43 55.0 0.14 44 55.3 0.14 45 55.7 0.14 46 56.0	20	32.9	0.53
23 42.4 0.30 24 43.8 0.27 25 45.0 0.25 26 46.0 0.23 27 46.9 0.21 28 47.7 0.20 29 48.4 0.19 30 49.0 0.18 31 49.6 0.18 32 50.2 0.17 33 50.7 0.16 34 51.2 0.16 35 51.7 0.16 36 52.1 0.15 37 52.6 0.15 38 53.0 0.15 39 53.4 0.15 40 53.8 0.14 41 54.2 0.14 42 54.6 0.14 43 55.0 0.14 44 55.3 0.14 45 55.7 0.14 46 56.0 0.14 47 56.4 0.14 48 56.7 0.14 49	21	38.0	0.38

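### One blank item voids a PROMIS score, so Month 12 Pain Behavior change (SAP secondary endpoint 1) normally needs 40 answered items; the loss depends on a skip rate the plan does not give

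*SAP*

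**What the plan says.** SAP section 6 (Definitions and Terminology) states that for each PROMIS scale "raw scores are calculated by summing each individual question score". The sum is converted to a standard score through the Appendix B tables. It then adds: "The score is not valid if any items are missing".

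The SAP does not state the number of items. The Pain Behavior table in Appendix B begins "20 32.9 0.53 21 38.0 0.38" and ends at a raw score of 100.

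SAP 9.2.1 lists as its first secondary endpoint "The change from baseline of PROMIS Pain Behavior" score at Month 12, compared between groups by t-test. On the change score, SAP section 6 says: "Change from baseline will be calculated as post-baseline value – baseline value". On missing data, SAP 7.3 says: "Missing data will be imputed for the primary endpoint only" and "All other endpoints will be analyzed with the data available".

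Nothing else in either document softens the rule for PROMIS.

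**The concern.** A 20-item form with one blank still holds 19 answers, and the plan discards them all. Because the endpoint is a change score and is not imputed, a blank at baseline or at Month 12 takes the subject out of the comparison, on top of any dropout. A long scale is the most exposed to an all-or-nothing rule, although one blank there costs the least information.

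Blanks are plausible. The six Appendix B tables imply 6 + 3 + 8 + 8 + 8 + 20 = 53 PROMIS items per visit. The protocol describes electronic capture for the diaries only (3.6.5, 3.6.8) and states no forced completion for PROMIS. Protocol 3.10.2 also allows follow-up assessments of hard-to-reach subjects to be returned by mail.

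At stake are the precision of SAP secondary endpoint 1 and possibly its representativeness, if subjects who skip items differ from those who do not.

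**Working it through.** The plan gives no completeness figure for this endpoint, so there is nothing to reproduce. The check is what the rule implies over a range of assumed skip rates.

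**Items.** The lowest raw score is 20 and the highest is 100, a ratio of 5. The same ratio holds in the other five PROMIS tables (6–30, 3–15, and 8–40 three times). With items scored 1 to 5, Pain Behavior has 20 items, and a change score needs 2 × 20 = 40 answers.

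**Sample.** 86 randomised 1:1 gives 43 per arm (SAP 4 and 7.1).

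**Independent skips** at item rate p:
- form invalid = 1 − (1 − p)^20
- change score lost = 1 − (1 − p)^40
- standard error inflated by 1/√[(1 − p)^40]

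**Clustered skips.** I used a beta-binomial with correlation ρ. P(no blank in n items) = ∏ (b + i)/(a + b + i) for i = 0 to n − 1, where a = p(1 − ρ)/ρ and b = (1 − p)(1 − ρ)/ρ. Clustering is taken either within a form (n = 20, result squared) or within a subject (n = 40), with ρ from 0.05 to 0.30.

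| Assumed p | Form invalid | Change lost, independent | Of 86 | Left per arm | SE factor | Change lost, clustered |
|---|---|---|---|---|---|---|
| 0.5% | 9.5% | 18.2% | 16 | 35 | 1.11 | 3.6–13.0% |
| 1% | 18.2% | 33.1% | 28 | 29 | 1.22 | 7.0–24.4% |
| 2% | 33.2% | 55.4% | 48 | 19 | 1.50 | 13.6–42.9% |

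The counts are before dropout. Under independence, a 20% loss needs p = 1 − 0.80^(1/40) = 0.56%.

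**Power, for illustration only.** The documents give no power for this endpoint. Take an effect with 80% power at 43 per arm, two-sided 0.05: (1.960 + 0.842) × √(2/43) = 0.604 SD. With the independent-skip numbers per arm, power falls to 72%, 63% and 46%.

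**Baseline fallback.** SAP section 6 allows the most recent earlier pre-repair value if the baseline value is unavailable. With two pre-operative forms at p = 1%, q = 0.182 per form, and the loss is 1 − (1 − q²)(1 − q) = 1 − 0.967 × 0.818 = 20.9%.

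**Cost of one blank.** Suppose 19 items are answered and sum to 57. Pro-rating gives 57 × 20/19 = 60, a T-score of 60.8. The true total lies between 58 and 62 (blank item 1 to 5), which Appendix B converts to 60.1 and 61.5. The error is at most 0.7 points on a scale with SD 10.

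**The case against.** **The skip rate is unknown.** Subjects complete PROMIS at visits, just after staff review the diary with them (protocol 3.6.1, 3.6.8). Protocol 8.1 provides for quality-control checks on each data procedure. The SAP introduction refers to a data management plan and case report forms, which are not available here. Item-completeness checks could bring the loss near zero. This stands, and it is why no single loss figure should be taken as the expected one.

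**Independence is the least favourable case examined.** This stands. People who skip tend to skip several items, so the clustered column belongs beside the independent one.

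**The baseline fallback softens the rule.** This stands only in part. The schedules mark pain assessments at both Visit 1 and Visit 2. However, protocol 3.9.2 asks for PROMIS on the operative day only if it was not done at screening, so one pre-operative form is the usual case. The SAP also does not say whether an invalid score counts as unavailable.

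**FHSQ.** A reader might infer that the SAP contradicts itself, since for FHSQ it says "When fewer than 50% of responses for any one scale are missing, any missing values for that scale are assigned to the average value" (taken over the answered items), or that the FHSQ rule needs changing too because it can never operate on the two-item General Foot Health scale. The documents do not support either step. FHSQ is a linear rescaling, while PROMIS looks up a complete raw sum in a nonlinear table, so different rules are not inconsistent. Filling half of a two-item scale from its other item is debatable. It would recover only about 2%, 4% and 8% at the same skip rates (four answers, 1 − (1 − p)^4). No FHSQ change is part of this point.

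**Conclusion.** The point holds as a conditional one. Followed as written, the plan discards usable data on SAP secondary endpoint 1. The loss is 18%, 33% or 55% of change scores at assumed item-skip rates of 0.5%, 1% or 2% if skips are independent. It is about 4% to 43% across those rates if they cluster. At 1% it is about 21% under independence if two pre-operative forms exist and the fallback applies. All of this rests on assumed skip rates and on a 20-item count inferred from Appendix B.

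Three stronger readings are tempting and unsupported:
- That a third or more of subjects will be lost. No document gives a skip rate.
- That this endpoint suffers the largest loss. Nothing allows comparison with the endpoints built on daily pain and medication diaries.
- That being listed first gives the endpoint a gatekeeping role. SAP 8.2 declines Type I error control, and the step-down order in protocol 5.7.1 puts VAS first and PROMIS second.

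The primary VAS analysis is unaffected.

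**What to change.** Replace the sentence in SAP section 6 with a rule fixed before analysis. A PROMIS scale is scored when at least half of its items, or a stricter stated share, are answered. Scoring is either by response pattern or by pro-rating the raw sum (sum × items ÷ items answered, rounded) before the Appendix B conversion. The SAP should name one of the two. Scoring on complete items only is kept as a sensitivity analysis, and the number of forms with any blank item is reported by arm and visit.

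The half-answered threshold is a choice, not something the documents dictate. Under independent skipping, a 20-item scale would almost never fail it. Even counting 10 or more blanks as a failure, the share of change scores lost at a 5% skip rate is about 2 in 100 million. Forms left largely blank would still be lost.

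The cost is one scoring rule and one sensitivity analysis. The downside is that recovered scores are less precise and assume that skipped items resemble answered ones. That assumption weakens as more items are missing, which is the argument for a stricter share.

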Number of Subjects per Treatment Group: Enroll approximately 15 evaluable subjects in the pilot study. Enroll approximately 86 additional subjects for the randomized comparative study.

Duration of Study: Up to 13 months including screening period.

Inclusion Criteria:

Potential Subjects must:

- 1. Be able and willing to provide documented informed consent prior to the conduct of any study procedures;
- 2. Be an adult male or non-pregnant female ≥ 18 years of age;
- 3. Report baseline pain scores of >65mm on a 100mm Visual Analog Scale (VAS) at screening;
- 4. Have a documented diagnosis of symptomatic neuroma of at least one interdigital nerve in the foot which cannot be repaired to a distal nerve end;
- 5. Must have the of the following:
 - Pain with at least 3 of the following characteristics: burning, sharp, shooting, electric, parasthesias, numbness, cold intolerance;
 - Symptoms in a defined neural anatomic distribution
 - History of nerve injury or suspected nerve injury Must have at least 1:
 - Positive response to local anesthetic injection
 - US or MRI confirmation of neuroma
- 6. Be candidates indicated for surgery to address a symptomatic neuroma;
- 7. Have sufficient healthy soft tissue available to adequately cover the Axoguard® Nerve Cap;

- 8. In the surgeon's opinion, be likely to achieve complete resection of the symptomatic neuroma and be able to undergo implantation with the Axoguard[®] Nerve Cap or complete the neurotomy procedure in the control group;
- 9. Be willing and able to comply with all aspects of the treatment and evaluation schedule over a 12-month duration.

Exclusion Criteria:

Potential subjects must not:

- 1. Have undergone surgical treatment of pain from symptomatic neuroma in the target nerve(s)on three or more occasions;
- 2. Have biomechanical pathology and associated pain (such as plantar fasciitis, bursitis, sesamoid bone pain, tendinitis, etc);
- 3. Have a life expectancy of less than 12 months;
- 4. Have a history of or planned radiotherapy in the area of the end-neuroma;
- 5. be contraindicated for soft tissue implants.; this includes but is not limited to any pathology that would limit the blood supply; compromise healing or indicate the presence of a local infection;
- 6. Have a history of chronic ischemic conditions of the extremity;
- 7. Have a diagnosis of type 1 Diabetes Mellitus; or uncontrolled Type 2 Diabetes Mellitus (at the discretion of the investigator);

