3.5.2 Efficacy Endpoints

Primary Efficacy Endpoints

- 1. The change in VAS score at 3 months compared to baseline (pilot phase)
- 2. The change in VAS score at 12 months compared to baseline (comparative phase)

Secondary Efficacy Endpoints

- 1. The change in VAS score at 1, 3, 6, 9 and 12 months compared to baseline
- 2. The change in PROMIS® score at 1, 3, 6, 9 and 12 months compared to baseline
- 3. The change in FHSQ score at 1, 3, 6, 9 and 12 months compared to baseline
- 4. Changes in pain medication use at 1, 3, 6, 9 and 12 months compared to baseline
- 5. Rate of recurrence of symptomatic neuroma within 12 months

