 $X_{optimal}$ = Score of the optimal foot health

 $S_{optimal}$ = Highest score of the new scale

Foot Function:

 $X_{worst} = 20$

 $X_{optimal} = 4$

 $S_{optimal} = 100$

Foot Health:

 $X_{\text{worst}} = 10$

 $X_{\text{optimal}} = 2$

 $S_{\text{optimal}} = 100$

Footwear:

 $X_{\text{worst}} = 3$

 $X_{\text{optimal}} = 15$

[figure not shown]
 $S_{\text{optimal}} = 100$

Foot Pain:

 $X_{\text{worst}} = 20$

 $X_{\text{optimal}} = 4$

 $S_{\text{optimal}} = 100$

Daily Pain Diary

A daily pain diary will be provided to each subject at the Screening visit (V1) and a new diary will be dispensed to the subject at Visits 2 through 7 to track incidence, frequency, and severity of pain (using a 10-point scale) daily. The diary will be reviewed and collected at each study visit (by the site team with the subject) prior to completing the scheduled pain assessments (VAS/PROMIS). The diary will also help track the use of subject pain medicine administration by reminding the subject to complete the Daily Pain Medication Diary for any pain medication/treatment taken by the subject at the time of the foot pain.

Daily Pain Medication Diary

A Daily Pain Medication Diary will be provided to each subject to take home and complete each day and will be reviewed at all visits. The subject will present the medication diary at each study visit for review by the site team and a new diary will be dispensed to the subject at each visit. The diary will be used to summarize pain medications by any use.

Opioid pain medications taken will be converted to morphine milligram equivalent (MME) where such conversions are available to summarize pain medications by quantity of use. For opioid and non-opioid pain medications, the Medication Quantification Scale⁴ (MQS) conversion will be used to convert medications to a comparable score. The MQS is a broader approach to quantifying medication consumption that captures non-opioid classes of medications without an equivalency to morphine. Unlike MME, two factors (detriment weight and dosage level) multiplied together scale the medication to a single score. Additionally, drugs will be categorized according to type of medication and the quantity taken will be summarized.

Recurrence of Symptomatic Neuroma

Subjects will be assessed for recurrence of symptomatic neuroma at the 3, 6, 9, and, 12 Month visits. The assessment intervals for each visit are as follows:

- Month 3 Visit: 6 Weeks after Operative Day 0 until Month 3 Visit

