- Month 6 Visit: Month 3 Visit until Month 6 Visit
- Month 9 Visit: Month 6 Visit until Month 9 Visit
- Month 12 Visit: Month 9 Visit until Month 12 Visit

A subject is considered to have had a recurrence of symptomatic neuroma if all of the following conditions are met:

 Subject experiences a pain level greater than 1 on the 10-point scale of the daily pain diary at least one time during the assessment interval

- The average daily dose of morphine (mg/day) calculated using morphine equivalent dosing during the assessment interval is higher than the average daily dose during the baseline interval (between Screening visit and Operative Day 0)
- VAS pain score is higher at assessment visit than at baseline visit

Adverse Event

An AE is defined as any untoward event (including abnormal lab findings) experienced by a subject (whether or not considered product-related by the site Investigator or Sponsor) after the patient consents to participate in the trial. All AEs that occur during or after study product implantation/device insertion must be recorded in the subject's medical record and reported on the adverse event CRF.

Serious Adverse Events

A serious adverse event (SAE) is any untoward medical occurrence that occurs per the following definition.

- Results in death:
- Is immediately life threatening in the opinion of the site Investigator, the participant was at substantial risk of dying at the time of the event, or use or continued use of the device might have resulted in the death of the subject;
- Requires in-patient hospitalization or prolongation of existing hospitalization.
 Complications that occur during hospitalization are adverse events, and if a complication
 prolongs hospitalization, the event is considered serious. Emergency room visits that do
 not result in overnight hospital admissions should be evaluated for one of the other
 serious outcomes (e.g., life-threatening; required intervention to prevent permanent
 impairment or damage);
- Results in a Congenital Anomaly / Birth Defect suspect that exposure to the device prior to conception or during pregnancy may have resulted in an adverse outcome in the child; or
- Requires Intervention to Prevent Permanent Impairment or Damage medical or surgical
 intervention was necessary to preclude permanent impairment of a body function, or
 prevent permanent damage to a body structure, either situation suspected to be due to the
 use of the device.

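### The protocol asks for neuroma recurrence within 12 months, but the SAP compares arms only on recurrence status at Month 12

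*SAP*

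**What the plan says.** Protocol 3.5.2 lists, as the fifth secondary efficacy endpoint, "Rate of recurrence of symptomatic neuroma within 12 months". Protocol 5.7.1 places the recurrence rate in the step-down list without a time window or a method.

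The SAP supplies the rule in section 6, under Recurrence of Symptomatic Neuroma: "Subjects will be assessed for recurrence of symptomatic neuroma at the 3, 6, 9, and, 12 Month visits". It continues: "A subject is considered to have had a recurrence of symptomatic neuroma if all of the following conditions are met". The three conditions are:

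- diary pain above 1 at least once in the assessment interval;
- a mean daily morphine-equivalent dose in the interval above that of the screening-to-surgery period;
- for the VAS, "VAS pain score is higher at assessment visit than at baseline visit".

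The Month 3 interval starts six weeks after surgery. Each later interval starts at the previous visit, so the Month 12 interval covers only Month 9 to Month 12.

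SAP 9.2.1, endpoint 5, is "Recurrence of symptomatic neuroma at Month 12", compared between arms by Fisher's exact test. Its note adds: "Assessments at each visit will be independent". The SAP's own example is a subject with a recurrence at Month 3 and none at Month 6. The same section says that "all secondary endpoints will be summarized by visit with descriptive statistics by treatment group". SAP 7.4.2 makes the mITT population primary for secondary endpoints.

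**The concern.** The two documents name different quantities. The protocol asks how many subjects have a recurrence at some time in the year. The SAP compares how many are in recurrence at the last visit. An earlier recurrence is not carried forward, so a subject who met all three conditions at Month 6 and then improved, whether spontaneously, with medication or after a second operation, enters the tested proportion as no recurrence.

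The study title includes prevention of recurrent end-neuroma pain, and this is the endpoint that names recurrence. If the report gives only the Month 12 comparison and four separate by-visit proportions, the protocol's question has no direct answer in either arm. A reader could also take the Month 12 proportion for the 12-month recurrence rate, which it can only equal or understate when follow-up is complete.

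**Working it through.** The plan gives no recurrence rate, effect size or power for this endpoint, so there is no stated figure to reproduce. The check is whether the rules, applied as written, return the protocol's quantity.

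**1. The two definitions side by side**

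| | Protocol 3.5.2 | SAP 9.2.1, endpoint 5 |
|---|---|---|
| Window | Any time up to Month 12 | Month 9 visit to Month 12 visit |
| Earlier recurrence | Counts | Not carried forward |
| Test | None given for this endpoint | Fisher's exact test on Month 12 proportions |

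**2. One subject put through the SAP rule.** A recurrence needs diary > 1 AND dose > baseline dose AND VAS > baseline VAS; only 1 of the 8 true/false combinations qualifies. Take an invented subject with baseline VAS 80 mm (eligible under inclusion criterion 3, "Report baseline pain scores of >65mm on a 100mm Visual Analog Scale (VAS) at screening") and baseline dose 2 mg/day, whose pain returns by Month 6 and is then relieved:

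| Visit | Diary | Dose | VAS | Recurrence? |
|---|---|---|---|---|
| Month 3 | 0 | 0 | 20 | no |
| Month 6 | 8 | 12 | 90 | yes |
| Month 9 | 5 | 6 | 50 | no (VAS not above 80) |
| Month 12 | 2 | 0 | 25 | no |

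Endpoint 5 scores this subject no. Recurrence within 12 months is yes.

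**3. Why by-visit proportions do not give the cumulative rate.** Let r3, r6, r9 and r12 be the numbers in recurrence at each visit in an arm of N. The number C with at least one recurrence is known only to satisfy

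max(r3, r6, r9, r12) ≤ C ≤ min(N, r3 + r6 + r9 + r12).

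N = 86/2 = 43, from SAP 7.1 and the 1:1 ratio. With one event at every visit (assumed), C runs from 1 (the same subject) to 4 (four subjects), that is 1/43 = 2.3% to 4/43 = 9.3%. The overlap between visits decides it, and the by-visit summaries do not show the overlap.

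**4. What the added analysis could do to the test.** Counts are assumed, 43 per arm, cap v control, two-sided Fisher. The added events are subjects with an earlier recurrence or a re-operation who are scored no at Month 12.

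| Month 12 only | p | Events within 12 months | p |
|---|---|---|---|
| 1 v 1 | 1.00 | 1 v 3 | 0.62 |
| 1 v 2 | 1.00 | 2 v 7 | 0.16 |
| 2 v 3 | 1.00 | 3 v 11 | 0.038 |

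Only the last row, with eight added events in one arm and one in the other, crosses 0.05. Swapping the arms gives the same p-values, so the documents imply no direction.

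**The case against.** The strongest reply is that status at each visit is a deliberate choice. The SAP says so and gives an example, and a subject whose pain has been relieved by Month 12 is correctly scored no under that definition. This stands, and it is why the Month 12 test should be kept. It does not make endpoint 5 the quantity named in protocol 3.5.2.

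A reader might go further and infer that the rule misclassifies re-operated subjects and so hides a material share of recurrences. The documents do not support that. They give no re-operation rate, so any such percentage would be assumed. A re-operated subject who meets all three conditions at Month 12 is counted, and one who withdraws is missing under SAP 7.3 rather than scored no. The mismatch also exists without any re-operation.

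Other planned analyses cover part of the ground:

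- By-visit summaries show an earlier recurrence if all three conditions held at that visit. SAP 9.2.1 also mentions a comparative analysis alongside them, which could be read as a test at every visit. Even so, these would be four separate visit-status comparisons.
- Endpoint 6 compares the area under the diary and VAS scores over 12 months. It captures the pain burden of an episode between visits but yields no recurrence rate.
- The per-protocol set could at most exclude a re-operated subject, and adverse event listings may show the operation. Neither counts a recurrence.

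SAP 9.4 and Appendix A are empty in the public copy, and protocol 5.8.3 appears only in the table of contents. A cumulative analysis may sit there, so its absence cannot be asserted. Finally, this is one of six secondary endpoints and plays no part in the definition of study success in protocol 5.10. That limits its weight, not its correctness.

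**Conclusion.** The point holds as a mismatch between the protocol's endpoint and the SAP's comparison. Subjects with a recurrence at Month 3, 6 or 9 that no longer meets the criteria at Month 12 count as no recurrence in the tested proportion, and the planned summaries cannot recover the rate within 12 months. This rests on the text alone.

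The size is unknown. The counts in the working are illustrations. They suggest that the reported rates would change more readily than the test result, which may seldom change. The primary analysis and the study success criterion are unaffected. How strict the three conditions are for someone whose pain returns to a level at or below a high baseline is a separate question, not raised here.

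**What to change.** Keep the Month 12 definition and its Fisher test, and add to SAP 9.2.1:

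1. **Recurrence within 12 months:** the three section 6 criteria met at any of Months 3, 6, 9 or 12, compared between arms by Fisher's exact test on the same population as endpoint 5. Label it supplementary. Report by arm how many subjects without an event were not followed to Month 12, since their status is incomplete.
2. **Target-nerve re-operations for pain or neuroma by Month 12:** a separate descriptive line by arm, with a sensitivity version of item 1 that counts them as recurrences. State that the surgeon is not blinded (protocol 3.7.1) and that some operations may reflect pain that never resolved. For these reasons re-operation should not enter the main any-visit definition.

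If a blanked section already holds this analysis, endpoint 5 need only refer to it.

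The any-visit analysis uses data already collected and costs a short paragraph and one table. Its rates will be equal to or slightly higher than those at Month 12. It inherits one limit: VAS is checked only at visits, so an episode that starts and resolves between two visits is still missed. The re-operation line needs the date and reason of any second operation in both arms; the action-taken item in adverse event recording (protocol 4.5) is a possible source.
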